- The number of Primary Analysis Cohort subjects enrolled per month will average 5 (1st month), 7 (2nd month), 11, 24, 35, 43, 51, 56, 60, 60, 60...
- Daily enrollments follow a Poisson distribution with an average of $x/30$, where x is the average number of enrollments in that month. This allows multiple ablation procedures in a day.
- 50% of enrollments are persistent AF subjects, and the other 50% are paroxysmal AF subjects
- 12-month effectiveness rate = 68% (A weighted average 12-month effectiveness was calculated at the bottom of the Table 15, resulting in an average effectiveness rate of 73.2%. Only three of the studies utilized weekly TTM (similar to the weekly patient activated ambulatory monitoring requirement), so due to the additional arrhythmia monitoring and a more stringent endpoint definition in PULSED AF, the 12-month paroxysmal AF effectiveness point estimate for this study has been set to 68%.)
- 6-month effectiveness rate = 79% (based on past studies (Table 15), the 6-month rate is approximately 11% higher than 12-month rate)
- 2% of patients will have an acute failure and these will occur on the first day post-ablation procedure
- Chronic failures (AF recurrence) occur either in the 3-6 month period or in the 6-12 month period, based on the assumed 68% and 79% numbers above.
- A patient with a chronic failure in the 3-6 month period has an equal chance of that failure occurring any day between 91 and 182 days post-ablation procedure
- A patient with a chronic failure in the 6-12 month period has an equal chance of that failure occurring any day between 184 and 364 days post-ablation procedure
- 5% attrition from ablation (drop out) procedure to 12 months
- Attrition occurs uniformly from 1-364 days post-ablation procedure
- [REDACTED]

Given the above assumptions, for the Paroxysmal AF arm of the study, a sample size of 165 Primary Analysis Cohort subjects is required.

To ensure proper characteristics of the study, especially alpha-level, the simulation program was rerun with all of the above assumptions (including the sample size of 165 subjects) the same, except that the assumed 12-month effectiveness rate was set to the null hypothesis rate of 55% (and 6-month effectiveness rate to 66%). [REDACTED]

[REDACTED] This meets the goal of having overall alpha being less than 2.5%.

Assumptions (Persistent Arm)

- The overall alpha will be 0.025, [REDACTED]
- Power=90%
- The number of Primary Analysis Cohort subjects enrolled per month will average 5 (1st month), 7 (2nd month), 11, 24, 35, 43, 51, 56, 60, 60, 60...
- Daily enrollments follow a Poisson distribution with an average of $x/30$, where x is the average number of enrollments in that month. This allows multiple ablation procedures in a day.
- 50% of enrollments are persistent AF subjects, and the other 50% are paroxysmal AF subjects
- 12-month effectiveness rate = 54% (A weighted average 12-month effectiveness was calculated at the bottom of Table 16, resulting in an average effectiveness rate of 59.5%. Due to the additional arrhythmia monitoring and more stringent endpoint definition in PULSED AF, the 12-month persistent AF effectiveness point estimate for this study has been set to 54%.)
- 6-month effectiveness rate = 72% (based on past studies (Table 16), the 6-month rate is approximately 18% higher than 12-month rate)
- 2% of patients will have an acute failure and these will occur on the first day post-ablation procedure
- Chronic failures (AF recurrence) occur either in the 3-6 month period or in the 6-12 month period, based on the assumed 54% and 72% numbers above.
- A patient with a chronic failure in the 3-6 month period has an equal chance of that failure occurring any day between 91 and 182 days post-ablation procedure
- A patient with a chronic failure in the 6-12 month period has an equal chance of that failure occurring any day between 184 and 364 days post-ablation procedure
- 5% attrition from ablation (drop out) procedure to 12 months
- Attrition occurs uniformly from 1-364 days post-ablation procedure

Given the above assumptions, for the Persistent AF arm of the study, a sample size of 150 Primary Analysis Cohort subjects is required.

To ensure proper characteristics of the study, especially alpha-level, the simulation program was rerun with all of the above assumptions (including the sample size of 150 subjects) the same, except that the assumed 12-month effectiveness rate was set to the null hypothesis rate of 40% (and 6-month to 58%). [REDACTED]

[REDACTED] This meets the goal of having overall alpha being less than 2.5%.

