8.6.2. Persistent AF Cohort

Up-titration of the Class I or III antiarrhythmic medication dose is allowed only in the 90-day post-procedure blanking period.

Class I and III antiarrhythmic medication use after the 90-day post-procedure blanking period:

- Subjects are allowed to remain on Class I or III antiarrhythmic medications at or lower than the historic maximum ineffective dose (prior to the ablation procedure) after the 90-day post-procedure blanking period.
- Re-initiation, at any point during follow-up, of a Class I or III antiarrhythmic medication that was failed or was not tolerated prior to the ablation procedure at any dose will be considered a primary endpoint failure.
- Initiation of a new Class I or III antiarrhythmic medication after the 90-day post-procedure blanking period will be considered a primary endpoint failure.
- Remaining on a dose higher than the historic maximum ineffective dose (prior to the ablation procedure) after the 90-day post-procedure blanking period will be considered a primary endpoint failure.

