Treatment success is defined as freedom from treatment failure. The study requires 24-hour Holter monitoring at 6 and 12 months in addition to weekly and symptomatic patient activated ambulatory monitoring transmissions from 3 through 12 months, and 12-lead ECGs at all follow up visits. Treatment failure is defined as any of the following components:

- Acute procedural failure (see definition below)
- Documented AF/AT/AFL on Holter/patient activated ambulatory/12-lead ECG after the 90-day post-ablation blanking period
- Minimum of 30 seconds on Holter/patient activated ambulatory or 10 seconds on 12-lead ECG recording
- Note: Documented occurrence and treatment of typical right-sided cavotricuspid isthmus dependent atrial flutter is not considered a failure.
- Any subsequent AF surgery or ablation in the left atrium, except for repeat PVI ablations using PFA within the 90-day blanking period.
- Direct current cardioversion for atrial tachyarrhythmia recurrences after the 90-day blanking period.
- Class I or III antiarrhythmic drug (AAD) dose increase from the historic maximum ineffective dose (prior to the ablation procedure) or initiation of a new Class I or III AAD after the 90-day blanking period. Note: remaining on the same pre-ablation dose or decreased dose of a previously failed or not tolerated Class I or III AAD after the 90-day blanking is not considered a failure.

Blanking period is defined as the first 90 days after the index ablation procedure. Recurrences of atrial arrhythmias during the blanking period will not be counted in the determination of the first clinical failure for the primary endpoint. Within the blanking period, recurrent arrhythmias can be managed with antiarrhythmic drugs or cardioversions. Titration of Class I and III antiarrhythmic medications are allowed during the blanking period.

Acute procedural failure is defined as:

- Inability to isolate all accessible targeted pulmonary veins (minimally assessed for entrance block and, where assessable, exit block) during the index procedure
- Ablation using a non-study device to isolate any pulmonary vein

Analysis Methods

The probability of a subject achieving effectiveness success at 12 months (365 days) will be estimated using survival analysis, the Kaplan-Meier method. The standard error will be approximated using Greenwood's formula. A two-sided 95% log-log confidence interval for the probability will be constructed.

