ⁱⁱ 6-month effectiveness rates are estimated from survival curves published in literature

Rationale for Performance Criteria (Persistent)

The choice of acceptable effectiveness performance criteria for persistent AF with 12-month follow-up data is selected based on the 2017 HRS/EHRA/ECAS Expert Consensus Statement on Catheter and Surgical Ablation of Atrial Fibrillation, which provides recommendations for success rates in clinical trials. The recommendation for evaluating the effectiveness of a treatment for persistent AF is as follows: *"If minimum chronic success rate is selected as an objective effectiveness endpoint for a clinical trial, we recommend that the minimum chronic acceptable success rate for persistent AF at 12-month follow-up is 40%."*³

Additionally, there is mounting evidence in published literature on the use of catheter ablation in the treatment of persistent AF. Figure 6 and Table 16 display a summary of published literature where the search criteria were publications of large multi-centered studies where the therapy was the use of catheter ablation (RF ablation or cryoablation) for a PVI-only approach for persistent AF. The summary includes study results published as manuscripts in peer reviewed medical journals. Varying rates in 12-month effectiveness have been observed. Similarly, variations in definitions of primary effectiveness and variations in arrhythmia monitoring have been utilized. The PULSED AF study design has an aggressive definition of primary persistent AF effectiveness (requiring acute success; and disallowing re-ablations, AAD dose increase from the historic maximum ineffective dose, or initiation of new AAD) and a more rigorous study design (requiring weekly patient activated ambulatory monitoring through 12 months).

To test a novel catheter ablation technology under these study design requirements, the Expert Consensus Statement recommended OPC of 40% provides a reasonable margin to compare the PFA system against ablation technologies currently used to treat persistent AF.

Figure 6: Current 12-Month Effectiveness Rates in Catheter Ablation Technologies for Persistent AF

[figure not shown]

Table 16: Summary of Published Literature on Catheter Ablation for Persistent AF

Reference	Design	Sites	Subjects (Ablation Type)	Subject Monitoring (When/How)	Effectiveness Endpoint Assessment	Acute Procedural Success	6M Effectiveness ⁱ	12M Effectiveness ⁱ

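### Persistent arm: the antiarrhythmic-drug failure component is not consistent between 8.6.2, 12.2.3 and its rationale for drug changes made inside blanking and kept past day 90

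*Combined protocol and SAP*

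**What the plan says.** The persistent-arm drug component appears in three places.

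- **12.2.3, persistent endpoint (same rule in the Synopsis).** One sentence holds two failure limbs. The dose limb is a "Class I or III antiarrhythmic drug (AAD) dose increase from the historic maximum ineffective dose (prior to the ablation procedure". The new-drug limb comes second and ends with the only time qualifier: "or initiation of a new Class I or III AAD after the 90-day blanking period". What is expressly not a failure is narrow: "Note: remaining on the same pre-ablation dose or decreased dose of a previously failed or not tolerated Class I or III AAD". During blanking, "Within the blanking period, recurrent arrhythmias can be managed with antiarrhythmic drugs or cardioversions"; the same paragraph goes on to say that "Titration of Class I and III antiarrhythmic medications are allowed during the blanking period".
- **8.6.2.** Up-titration is permitted only in blanking. "Remaining on a dose higher than the historic maximum ineffective dose (prior to the ablation procedure) after the 90-day post-procedure blanking period" is a primary endpoint failure. For new drugs: "Initiation of a new Class I or III antiarrhythmic medication after the 90-day post-procedure blanking period will be considered a primary endpoint failure".
- **12.2.3, Rationale for Performance Criteria (Persistent).** The endpoint is called aggressive because of "disallowing re-ablations, AAD dose increase from the historic maximum ineffective dose, or initiation of new AAD", with no time limit attached.

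In the paroxysmal arm, any Class I/III use after day 90 is a failure, so the question does not arise there.

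**The concern.** The 12.2.3 wording turns on when a drug change is made, whereas part of 8.6.2 turns on what the subject is taking after day 90. A subject with an early recurrence may have a drug started or escalated on, say, day 60 and stay on it to month 12. If monitoring is then clean, that subject may count as an ablation success while on added drug therapy.

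The arm is single, unblinded and tested against a fixed 40% goal, so no control group absorbs such misclassification. The only sensitivity analysis in 12.2.3 addresses subjects who leave early, not drug use. Section 4 sends the reader to Section 12 for endpoint definitions, but nothing withdraws the explicit endpoint statements in 8.6.2.

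**Working it through.** **Step 1: the texts side by side, for changes made inside blanking and kept past day 90.**

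| Case | 8.6.2 | 12.2.3 and Synopsis | Rationale in 12.2.3 |
|---|---|---|---|
| Dose raised above historic maximum, kept | Failure | Depends on reading | Described as disallowed |
| Never-used Class I/III drug started, continued | No failure limb met | No failure limb met | Described as disallowed |

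*Dose row.* The time qualifier in 12.2.3 stands at the end of the sentence. If it governs both limbs, an increase on day 60 is outside the rule, and 12.2.3 does not fail a subject whom 8.6.2 fails. If it governs only the new-drug limb, an increase inside blanking is itself a failure, which sits badly with the permission to titrate then. Neither reading matches 8.6.2 cleanly.

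*New-drug row.* The drug was not initiated after day 90, it has no historic maximum dose to exceed, and it is not a re-initiation of a failed drug. Section 8.6 bars amiodarone after ablation but leaves other Class I/III agents open.

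Section 8.6.2 also fails re-initiation of a failed or untolerated drug at any time in follow-up, a limb absent from 12.2.3. That is a separate mismatch and is not counted here.

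**Step 2: reproduce the plan's figure.** Inputs from 12.2.3: n = 150; 12-month success 54%; 6-month success 72%; 2% acute failure on day 1; later failures uniform on days 91–182 and 184–364; 5% uniform attrition; goal 40%; Kaplan-Meier with Greenwood variance and a two-sided 95% log-log bound. The alpha-spending details are redacted, so final one-sided levels of 0.025, 0.0225 and 0.02 were tried. Simulated power (10,000 trials each) is 91.5%, 91.1% and 89.5%. At a true 40% (6-month 58%) and level 0.025, the pass rate is 2.2%. The sample size of 150 is reproduced and is not in question.

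**Step 3: the pass mark without censoring.** Lower bound = S^exp(1.96·√g / |ln S|), with g = (1 − S)/(nS).

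- 72/150: S = 0.4800, √g = √(0.52/72) = 0.0850, |ln S| = 0.7340; exponent exp(0.2269) = 1.2548; bound 39.8%, goal missed.
- 73/150: S = 0.4867, √g = √(0.5133/73) = 0.0839, |ln S| = 0.7202; exponent exp(0.2282) = 1.2564; bound 40.5%, goal met.

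The planned 54% is 81/150, so the margin is 81 − 73 = 8 subjects.

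**Step 4: illustration.** Let m be the percentage of subjects scored as success under a lenient reading and as failure under the rule in the rationale. The documents give no value for m; those below are assumptions. The 6-month rate is kept 18 points above the 12-month rate, as in the plan, with no interim adjustment. The ranges cover two simulations of 5,000 and 4,000 trials per scenario.

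| m | Subjects of 150 | Rate as scored, if 40% under the rationale's rule | Chance of meeting goal |
|---|---|---|---|
| 0 | 0 | 40% | about 2% |
| 2 | 3 | 42% | 6–7% |
| 5 | 7–8 | 45% | 21% |
| 10 | 15 | 50% | 66% |

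Conversely, if the planned 54% is the lenient-reading rate, power under the stricter rule is about 81% at m = 2, 56% at m = 5 and 15% at m = 10 (4,000 trials each).

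**The case against.** The strongest reply has four parts.

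1. *8.6.2 already fails the kept higher dose, and 12.2.3 never calls that subject a success.* Its note protects only the same or a lower dose, and a dose increase from a historic reference could be read as being above that reference after day 90. This reading is possible and would remove the dose conflict. It is not what the sentence plainly says, and a programmer working from 12.2.3 alone could score it either way.

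2. *A new drug begun in blanking is not expressly allowed after day 90.* The 8.6.2 permission is limited to doses at or below the historic maximum, and the 12.2.3 note to drugs previously failed or not tolerated. That is right: it is a gap, not a permission. But success is defined as freedom from the listed failures, so an unlisted exposure defaults to success.

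3. *The benchmark is more lenient.* None of the four persistent-AF studies in Table 16 lists an antiarrhythmic-drug criterion, and the 40% goal is taken from a consensus recommendation. This stands, and it limits any claim that the comparison with published rates is unfair. It does not cure the internal inconsistency. The plan also relies on a more stringent definition when it lowers its assumed rate from the 59.5% literature average to 54%.

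4. *The affected group may be small.* Amiodarone is barred, re-initiated failed drugs count as failures under 8.6.2, and subjects must still be free of documented arrhythmia on weekly transmissions, two Holters and ECGs, and meet every other component. This stands: m is unknown and may be low.

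**Conclusion.** The point holds as an inconsistency plus a gap in a primary endpoint. A dose raised in blanking and kept can be scored differently by section. A never-used drug started in blanking and continued is caught by neither section, although the rationale describes new drugs as disallowed. The size is unknown. The figures of about 7%, 21% and 66% rest on assumed rescoring of 2%, 5% and 10%, a true rate of exactly 40% under the rationale's rule, n = 150 and a two-sided 95% log-log bound without interim adjustment.

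Stronger readings that a reader might infer are not supported:

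- *The plan ignores new drugs.* It does not; both sections fail one initiated after day 90.
- *The bias always favours success.* This is true of the new-drug gap and of the lenient dose reading only. If the time qualifier covers only the new-drug limb, increases inside blanking become failures and success falls.
- *The test's type I error is inflated.* For the endpoint as scored, simulated type I error is about 2.2%. The higher figures are pass rates when the scored rate is truly 42%, 45% or 50%. They show how far the answer depends on the definition.
- *The sample size is wrong.* It is reproduced.

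**What to change.** Before the endpoint is analysed, reconcile the Synopsis, the persistent endpoint in 12.2.3, section 8.6.2 and the persistent rationale into one scoring rule. It should state how each of the following is scored after day 90, and on what date any failure falls, since the Kaplan-Meier analysis needs one:

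- a dose raised above the historic maximum in blanking and kept;
- a new Class I/III drug started in blanking and continued.

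The choice of rule, and what may be prescribed during blanking, is for the sponsor.

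Add one supplementary Kaplan-Meier estimate for the persistent arm that counts both exposures after day 90 as failures, to show whether the conclusion depends on the rule chosen.

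The cost is wording in four places and one extra run. Section 8.6 already collects drug name, dose, dosage changes with reasons, and start and stop dates. The downside is that the success rate may be slightly lower in the supplementary analysis, and in the primary one if the sponsor adopts the stricter rule.

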8.1. Schedule of Events

Data collection requirements are summarized in Table 7, below.

Table 7: Study Procedures and Data Collection per Subject Visit

	Baseline	Procedure	Discharge	30 Day	3 Month ¹	6 Month ¹	12 Month	Unscheduled	Repeat Ablation
Informed Consent	X								
Inclusion/Exclusion Criteria	X								
Medical History	X								
Physical Exam	X								
Pregnancy Screen ²	X								
AAD & Anticoagulation Medication Review	X		X	X	X	X	X	X	X
Arrhythmia Symptom Review	X			X	X	X	X	X	X
12 Lead ECG	X		X	X	X	X	X	X	
NIHSS Assessment	X		X						X
Cardiac CT Scan or MRI ³	X				X	X	X		
AFEQT & EQ-5D-5L	X					X	X		
Transthoracic Echocardiogram (TTE) ⁴	X								
Transesophageal Echocardiogram (TEE) ⁵	X								
INR Assessment ⁶	X								
Ablation Procedure Data		X							X
24h Continuous Monitoring with Holter						X	X		
Patient Activated Ambulatory ECG Monitor ⁸					Weekly and symptomatic episodes				
Adverse Events	As they occur								
Device Deficiencies	As they occur								
Study Deviations	As they occur								

Notes:

¹ Multiple modes of data collections may be employed to support the collection of required visit data at the 3- and 6-month visits such as: In office patient clinic visit, direct to patient contact (i.e. telephone, email, mail contact, etc.), and remote technology transmissions/uploads.

² Female subjects of child bearing potential only.

³ Baseline and 3-month cardiac CT/MRI required for all subjects in the Pilot Phase. For the Pivotal Phase, cardiac CT/MRI is required only for subjects with suspected PV stenosis at 3-, 6- or 12-month visits and who did not undergo cardiac CT/MRI at a previous visit.

⁴ Only required if data not available from within 6 months prior to consent date.

⁵ TEE must be performed in all subjects. The TEE should occur within one day (on the day of or within the day prior to) the planned ablation procedure.

⁶ Subjects taking a vitamin K antagonist (VKA) are required to have a therapeutic INR (2-3.5) on the day of the planned ablation procedure. INR assessment is not required for subjects on other types of anticoagulants.

⁸ Subjects shall submit ECG transmissions weekly and whenever symptoms occur after the post-ablation blanking period through 12-month follow-up.

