8.9. Scheduled Follow-up Visits

After receiving notice of a completed index ablation procedure, Medtronic will provide the target dates and windows for each visit to the site. Should a subject miss a visit or the visit fall outside the pre-specified window, a study deviation must be reported and the original follow-up schedule maintained for subsequent visits.

Data analyses include follow-up visits, regardless of whether the visit occurs within the window. Therefore, a late visit is preferred over a missed visit but must be accompanied by a deviation. Follow-up visit windows are listed in Table 8 and are based on days after the index ablation procedure.

Table 8: Follow-up Schedule

Occurrence/ Visit	Window (Calculated days after the ablation procedure)	
	Window Start	Window End
Enrollment/Baseline ¹	-30 days	Day 0
Index PFA System Ablation Procedure	Day 0	Day 0
30 day	30 days	44 days
3 month	91 days	105 days
6 month	183 days	197 days
12 month	365 days	395 days

¹Note: if the time between the consent date and the procedure exceeds 30 days, the subject must be re-evaluated against inclusion and exclusion criteria to ensure they still qualify for the study.

Multiple modes of data collections may be employed to support the collection of required visit data at the 3- and 6-month visits such as: In office patient clinic visit, direct to patient contact (i.e. telephone, email, mail contact, etc.), and remote technology transmissions/uploads.

The following information is required to be collected at the follow-up visits:

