12.2.2. Primary Safety Objective

Demonstrate an acceptable safety profile of PVI ablation with the PFA system.

Hypothesis

The following hypothesis will be tested in a one-sided test:

Ho: PS \geq 13%

Ha: PS < 13%

Where PS is the probability of a safety event through 6 months.

Endpoint Definition

The primary safety endpoint definition, as follows, is identical for each arm (paroxysmal AF and persistent AF) of the Pivotal Phase.

The following PFA system-related and ablation PFA procedure-related serious adverse events (SAEs), as adjudicated by the Clinical Events Committee (CEC), will be considered a primary safety event:

Within 6 months post-ablation:

- Pulmonary vein stenosis (>70% diameter reduction)
- Phrenic nerve injury/diaphragmatic paralysis (ongoing at 6 months)
- Atrioesophageal fistula

Within 30 days of ablation procedure:

- Cardiac tamponade/perforation
- Cerebrovascular accident
- Major bleeding requiring transfusion
- Myocardial infarction
- Pericarditis requiring intervention
- Transient ischemic attack
- Vagal nerve injury resulting in esophageal dysmotility or gastroparesis
- Vascular access complications requiring intervention
- Death
- Any PFA system-related or PFA procedure-related cardiovascular and/or pulmonary adverse event that prolongs or requires hospitalization for more than 48 hours (excluding recurrent AF/AFL/AT)

Analysis Methods

The probability of a safety event at 6 months (183 days) will be estimated using survival analysis, the Kaplan-Meier method. The standard error will be approximated using Greenwood's formula. A two-sided 95% log-log confidence interval for the probability will be constructed.

For every treated subject, day 0 is defined as the day of the index ablation procedure. For subjects with a safety event, the survival date will be set to the onset date of the safety event. For subjects without a safety event, those subjects will be censored at the last study contact date recorded on CRF which may include the last study visit, the exit date, or death date. If a subject without a safety event is lost to follow-up, the censoring date will be set to the last known study visit date.

Safety events related to a repeat ablation procedure with the PFA system will not be counted as safety events against the primary safety objective. However, all repeat PVI ablations using the PFA system and the safety events associated with them will be reported separately.

Performance Requirements

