For every treated subject, day 0 is defined as the day of the index ablation procedure. For subjects with treatment failure, the survival date will be set to the date of the treatment failure. For subjects without treatment failure through 12 months, those subjects will be censored at the last study contact date recorded on a CRF which may include the last study visit, the last weekly patient activated ambulatory, the exit date, or death date. If a subject without a treatment failure is lost to follow-up, the censoring date will be set to the last known study visit date.

For the component of the endpoint, documented AF/AT/AFL, if this documentation resulted from rhythm monitoring occurring at the 12-month visit within the 12-month visit window, the date of recurrence will be set to 365 days from the study ablation procedure so that these events will be counted as treatment failures in the 12-month Kaplan-Meier analysis.

Sensitivity Analyses

A sensitivity analysis will be conducted to estimate the potential impact of subjects with less than 12 months of follow-up at the final analysis. The mortality rate in this patient population is anticipated to be low. The total assumed attrition rate through one year is 5%. Because the primary endpoint will be tested using survival methods, all treated subjects are included in the primary analysis, and therefore no subjects will have complete missing data. For subjects that exit early, a tipping point analysis will be conducted to estimate the potential impact of subjects with less than 12 months of follow-up. These subjects will be defined as subjects with partial data. The tipping point analysis methods will be as follows. For each subject with less than 12 months of follow-up, each subject will be set to treatment failure (failure date set to date of study exit). The 12-month Kaplan-Meier estimate will be re-calculated with the earliest (closest to index ablation) sequentially added to the Kaplan-Meier analysis, and the results presented in table format. The tipping point will be defined as the number of additional failures in which the performance goal (55% for paroxysmal and 40% for persistent) is crossed by the lower 95% confidence bound.

Performance Requirements

If the lower bound of the confidence interval (coverage level determined by the alpha spending function) is greater than the performance goal (55% for paroxysmal and 40% for persistent), the objective will be considered met.

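### Censoring lost-to-follow-up subjects at their last visit, while still counting AF recorded after it, biases 12-month success slightly downward; the effect is minor and conservative

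*Combined protocol and SAP*

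**What the plan says.** Section 12.2.3 (Analysis Methods) sets three dating rules for the primary effectiveness endpoint.

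- Failures: "For subjects with treatment failure, the survival date will be set to the date of the treatment failure". Nothing limits this to failures found at or before the last visit.
- Failure-free subjects in general are censored at the last contact on a CRF, "which may include the last study visit, the last weekly patient activated ambulatory, the exit date, or death date".
- Failure-free subjects who are lost: "If a subject without a treatment failure is lost to follow-up, the censoring date will be set to the last known study visit date".

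Rhythm data continue between visits. Table 7 (Section 8.1, note 8) states: "Subjects shall submit ECG transmissions weekly and whenever symptoms occur after the post-ablation blanking period through 12-month follow-up". Under Section 8.11 the core lab adjudicates these recordings for the primary effectiveness objectives. In Table 8 (Section 8.9) the visit windows open at days 30, 91, 183 and 365, and the six-month window closes at day 197, so no visit is scheduled between then and day 365. Section 8.19 lists loss to follow-up separately from withdrawal and makes all data up to exit available for analysis.

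The sample-size assumptions are 5% attrition by 12 months, and "Attrition occurs uniformly from 1-364 days post-ablation procedure". Section 12.2.2 carries a parallel sentence for safety: "If a subject without a safety event is lost to follow-up, the censoring date will be set to the last known study visit date".

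**The concern.** Take a subject seen at month 6 who transmits for some weeks more and then disappears. If a strip in those weeks shows AF, the subject is a failure on that date. If every strip is clean, the subject leaves the risk set at the month 6 visit. The weeks after the visit count only when they contain an event. Kaplan-Meier requires censoring to be unrelated to outcome given survival so far, and this rule breaks that: the events stay in the numerator while matching event-free time is taken out of the denominator.

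Two subjects with identical visits and identical clean strips can also get different censoring dates, depending only on whether the exit is labelled as lost or withdrawn. The planned tipping-point analysis does not expose the problem. It turns early exits into failures at the exit date and does not vary the censoring date.

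At stake are the success estimate and its lower confidence bound in both arms, and some of the power on which 165 and 150 subjects were chosen.

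**Working it through.** **Inputs, all from 12.2.3 unless noted.** Paroxysmal: N = 165, success 79% at 6 months and 68% at 12, goal 55%. Persistent: N = 150, 72% and 54%, goal 40%. Acute failure 2% on day 1; later failures uniform over days 91-182 and 184-364; attrition 5%, uniform over days 1-364. Visits at days 30, 91 and 183 (Table 8). Not given in the documents, so assumed: the share of attrition that is lost to follow-up (25% to 100% tried), transmission until the day of drop-out, drop-out unrelated to rhythm, and a single look at one-sided 0.025, because the interim plan is redacted.

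**Formulas.** S = product of (1 - d/n) over event days to day 365. Standard error on the log-log scale: se = sqrt(sum of d/[n(n - d)]) / |ln S|. Lower bound = S^exp(1.96 se). The trial succeeds if this exceeds the goal.

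**Step 1, the mechanism by hand.** Take 1,000 paroxysmal subjects, 50 of them lost on day 364 and last seen on day 183. After day 183, 790 are failure-free and 110 will fail by day 364.

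- Censoring at day 364: 0.79 x (790 - 110)/790 = 68.0%.
- Rule as written: of the 50 lost, 50 x 0.68 = 34 are failure-free and go back to day 183, leaving 756 at risk with the same 110 events. 0.79 x (756 - 110)/756 = 67.5%.
- Last-visit censoring with later failures of lost subjects also ignored: 50 x 0.79 = 39.5 leave the 790, giving 750.5 at risk and 110 x 0.95 = 104.5 events. 0.79 x (750.5 - 104.5)/750.5 = 68.0%.

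Both symmetric rules are unbiased; the mixed one is not. For the persistent arm the rule as written gives 0.72 x (693 - 180)/693 = 53.3% against 54.0%. All losses on day 364 is the worst timing: -0.5 and -0.7 points.

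**Step 2, the plan's own figure.** Simulating the plan's model (10,000 trials per scenario) with censoring at drop-out gives power of 91.2% at 165 and 91.5% at 150, close to the stated 90%. In steps of 5, the smallest N above 90% is 160 (90.2%) and 145 (90.5%), one step below the plan. Spending alpha at interim looks could explain that: at a final alpha of 0.02, power at the planned N is 89.6% and 90.1%.

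**Step 3, the rule as written, on the same simulated trials.**

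| Attrition, share lost | Arm | Bias in success (points) | Power: drop-out censoring to rule as written |
|---|---|---|---|
| 5%, all | Paroxysmal | -0.21 | 91.2% to 90.2% |
| 5%, all | Persistent | -0.27 | 91.5% to 89.9% |
| 5%, half | Paroxysmal | -0.11 | 91.3% to 90.7% |
| 5%, half | Persistent | -0.13 | 91.4% to 90.8% |
| 5%, quarter | Paroxysmal | -0.05 | 91.2% to 91.0% |
| 5%, quarter | Persistent | -0.07 | 91.8% to 91.5% |
| 10%, all | Paroxysmal | -0.45 | 90.4% to 88.0% |
| 10%, all | Persistent | -0.57 | 90.8% to 87.8% |
| 20%, all | Paroxysmal | -1.0 | 88.7% to 82.1% |
| 20%, all | Persistent | -1.2 | 88.1% to 80.4% |

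Simulation error on one power figure is about sqrt(0.9 x 0.1/10,000) = 0.3 points. A separate run of 40,000 trials per cell, with visits at days 37, 98 and 190 and 5% all lost, gave 91.2% to 90.0% and 91.5% to 90.3%.

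**Step 4, type I error.** With true success at the goal and 5% all lost, the rejection rate moves from 1.8% to 1.5% (paroxysmal) and from 2.2% to 1.8% (persistent).

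**The case against.** The strongest defence is that a clean strip is not a clean endpoint. Failure also includes antiarrhythmic drug use or change, cardioversion and left-atrial ablation, and medication is reviewed at visits. The last visit is the last full assessment of the composite. Censoring at a later strip credits failure-free time on components nobody checked, which could push success upward. This stands. It supports last-visit censoring as a choice, but not combining it with failures counted after that visit.

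The size also depends on favourable modelling. The 5% is total attrition, and Section 8.19 names several other exit reasons. Section 8.18 anticipates missed transmissions, and Section 8.10 allows unscheduled visits; both would shorten the time discarded. These points stand and make the all-lost figures an upper case at 5% under uniform timing.

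A reader might infer that the sample-size simulation left this rule out, since it describes attrition only as uniform. The documents do not support that. The uniform assumption says when subjects leave, not how they are censored, and the Sample Size Calculation text says each simulated study received the stated primary analysis. In a 40,000-trial run with the rule as written and all attrition lost, power was 89.2% at 160 and 90.6% at 165, and 89.4% at 145 and 90.1% at 150, so the planned numbers are the ones that cross 90%. Redacted interim alpha could explain them equally well. Whether the rule was simulated cannot be determined.

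**Conclusion.** The rule is wrong as written: it makes censoring depend on outcome, and no other section corrects it. The consequence is minor. At the planned 5% attrition, success is understated by about 0.2 to 0.3 points and single-look power falls by about 1 to 1.6 points if every exit is a loss to follow-up. With 25% to 50% of exits lost, the figures are about 0.1 point and 0.2 to 0.6 points. It becomes material only near 10% lost. The direction is conservative, type I error is not inflated, and a positive result would not be put in doubt.

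Two stronger readings should be resisted. One is that the margin over 90% power is used up: that is the worst case on the share lost, and the interim alpha is not visible. The other is that the safety result is biased to a similar degree: the sentence in 12.2.2 has the same form, but rhythm strips do not bear on that endpoint and no effect on it has been shown.

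The figures rest on a single look, transmission up to drop-out, drop-out unrelated to rhythm, and scheduled visits only.

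**What to change.** Make the rule symmetric in 12.2.3, in one of two ways.

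1. Delete the lost-to-follow-up sentence and apply the plan's general rule to every failure-free subject, censoring at the last date rhythm was assessed, including the last weekly transmission read by the core lab.
2. Keep last-visit censoring for lost subjects and add that their failures after that visit are disregarded.

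Report whichever is not primary as a sensitivity analysis, and say why: a negative strip rules out the arrhythmia component but not drug use, cardioversion or ablation.

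The cost is about one sentence in the analysis methods and one extra Kaplan-Meier run per arm. Transmission dates are already in the core-lab data, and no further subjects or data collection are needed. The matching sentence in 12.2.2 may be aligned for consistency.
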